## **5.3. Study Endpoints**

Primary efficacy endpoint is met when OCT imaging has the equivalent or higher ranking of IVUS imaging of the visualization of vessel morphology and disease for:

- Layered structure – intima, media, external elastic lamina, and adventitia;
- Non-layered structure—presence of disease in the vessel structure;
- Abnormal physiology—dissection/tissue flap/false lumen, thrombus, calcium;
- Bifurcation of the vessel; and
- Frequency of artifacts.

Secondary efficacy endpoint is met when OCT imaging has the equivalent dimensions of vessel diameter and total luminal area as that determined with IVUS imaging.

Primary safety endpoint is freedom from diagnostic imaging procedure-related and device-associated adverse events, as reported by the physician.

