## **5. INVESTIGATIONAL PLAN**

### **5.1. Study Design Overview**

The purpose of this is a study to collect images of the same vessel segments using both the IVUS and OCT systems so that a comparison can be made of the two imaging modalities. IVUS and OCT images will be captured at identical positions within vessel segments. Continuous imaging will occur as the catheters are moved from distal to proximal endpoints established with a radiopaque marking tape attached to the subject's leg.

The trial will enroll up to 25 subjects diagnosed with peripheral arterial disease of the lower extremities, with the goal to acquire at least 115 matched images for analysis.

The images will be anonymized and given a unique identification prior to assessment by three radiologists (readers) for review. The readers will review the images and rank each for image clarity (using a visual analogue scale or VAS) and identification of vessel morphology and disease pre- and post-procedure.

The inclusion criteria for subjects are:

1. Subject is an adult ( $\geq 18$  years old); and
2. With suspected vascular disease that might be a candidate for IVUS; and
3. Reference vessel lumen is acceptable for use of the Pantheris and IVUS catheters as per visual angiographic estimation.
4. Successful diagnostic imaging and removal of the IVUS catheter with no adverse events.

The exclusion criteria are:

1. Subject, if female, is pregnant or breast feeding; or
2. Subject is unwilling to give informed consent.

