## **5.2. Sample Size Estimate**

When the sample size is 108 images of both the OCT and IVUS catheters, a two group 0.05 one-sided matched t-test will have 90% power to reject the null hypothesis that the test (OCT) and standard (IVUS) are not equivalent in favor of the alternative hypothesis that the two groups are equivalent. To obtain 108 vessel segment images at five images per subject, 22 subjects would be needed; however, recognizing that some images (~ 5%) may be of poor quality and illegible, 25 subjects should be enrolled and 115 images evaluated.

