### 6.3 Statistical Analyses

Statistical analyses will be carried out using StatView software (SAS Institute, Cary, NC). A  $p$  value  $< 0.05$  will be considered statistically significant. Matched Pairs  $t$ -Test will be performed to compare means and on paired samples to compare procedural data and complications associated with the imaging techniques. The mean values of the results of all readings of all readers will be calculated for comparison of image quality. Fisher's Exact Test will be used to compare proportions. The Mann-Whitney-Wilcoxon test will be applied for statistical comparison of the results for OCT and IVUS imaging. Interreader and intrareader reproducibility will be calculated by intraclass correlation (ICC) analysis in a two-way mixed model. Correlation of the mean values of the results of the quantitative measurements of all readers with both imaging modalities will be calculated as Pearson correlation coefficient.

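### The 90% power in section 5.2 is for one test, but section 5.3 reads most naturally as five items that must all pass, and no power is given for that rule

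*Combined protocol and SAP*

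**What the plan says.** Section 5.2 contains the only power statement. A one-sided 0.05 matched t-test on 108 images from each device "will have 90% power to reject the null hypothesis that the test (OCT) and standard (IVUS) are not equivalent". Equivalence is named as the alternative. The section does not say which score is tested, and it gives no margin, expected difference or standard deviation of the paired differences.

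Section 5.3 sets the success rule: "Primary efficacy endpoint is met when OCT imaging has the equivalent or higher ranking of IVUS imaging", followed by five items (wall layers, disease in the vessel structure, abnormal findings, bifurcation, artifacts). The fourth entry reads "Bifurcation of the vessel; and", so the list is conjunctive in form. No sentence says whether all items, any item or a combined score decides the endpoint.

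Section 6.2 grades the five items on separate scales of 4, 5, 5, 3 and 3 levels. Grade 1 is best on each. Readers also score image clarity on a visual analogue scale.

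Section 6.3 says "The mean values of the results of all readings of all readers will be calculated for comparison of image quality" and "The Mann-Whitney-Wilcoxon test will be applied for statistical comparison of the results for OCT and IVUS imaging". The averaging is over readings and readers; averaging over items is not mentioned, and no rule combines the five results.

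**The concern.** A power figure should belong to the rule that decides success. Here it belongs to one unnamed test, while the rule appears to need five results at once. Requiring all five does not inflate the type I error, but it lowers the chance of success unless the items are perfectly correlated. A sponsor reading section 5.2 would expect a 10% chance of missing the endpoint when the devices are truly equal. Under an all-must-pass rule that chance could be several times larger.

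Leaving the rule open has a second cost, because it could be chosen after the results are seen. If any one item were allowed to suffice, five independent tests at one-sided 0.05 would carry an error rate of up to 1 − 0.95^5 = 22.6%.

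**Working it through.** **Inputs from the documents.** One-sided alpha 0.05, power 90% and 108 pairs (section 5.2); five items (section 5.3).

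**Inputs not in the documents, so assumed.** Each item has 90% power at zero true difference, each has 108 gradable pairs, pairs are independent, and the five test statistics share a common correlation ρ between 0 and 1.

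**Step 1: the plan's own figure.** The 108 cannot be reproduced, because no margin or standard deviation is given. It can only be solved backwards for the margin in units of the SD of the paired differences:

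- Non-inferiority: (z0.95 + z0.90)/√108 = (1.645 + 1.282)/10.392 = 0.282 (0.283 with the t distribution).
- Two one-sided equivalence tests: (1.645 + 1.645)/10.392 = 0.317 (0.319 with the t distribution).

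These are possible unstated inputs, not confirmation. The subject count does follow: 108/5 = 21.6, so 22. For images, 108/0.95 = 113.7, so 114, close to the stated 115.

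**Step 2: joint power if all five must pass.** For independent items it is 0.9^5 = 0.590. For correlated items, with φ and Φ the standard normal density and distribution function:

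- Non-inferiority: ∫ φ(u) · Φ[(c + √ρ·u)/√(1−ρ)]^5 du, with c = z0.90 = 1.282.
- Equivalence: ∫ φ(u) · {Φ[(c − √ρ·u)/√(1−ρ)] − Φ[(−c − √ρ·u)/√(1−ρ)]}^5 du, with c = z0.95 = 1.645.

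| Assumed ρ | Non-inferiority | Two one-sided equivalence tests |
|---|---|---|
| 0 | 59% | 59% |
| 0.3 | 66% | 62% |
| 0.5 | 71% | 67% |
| 0.8 | 79% | 77% |
| 0.9 | 83% | 81% |
| 1 | 90% | 90% |

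A simulation of the non-inferiority column with 1,000,000 draws gave 0.591, 0.707 and 0.790 at ρ = 0, 0.5 and 0.8.

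**Step 3: chance of missing the endpoint at zero true difference.** For non-inferiority: 1 − 0.59 = 41% at ρ = 0, 1 − 0.71 = 29% at 0.5 and 1 − 0.79 = 21% at 0.8. For equivalence: 41%, 33% and 23%. Section 5.2 implies 10%.

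**Step 4: direction of the remaining assumptions.** Five images come from each subject, so positive within-subject correlation of the paired differences would lower these figures. An item that cannot be graded on every image (a bifurcation need not appear at each position) would have fewer than 108 pairs and less than 90% power. In the other direction, if OCT is truly better, per-item non-inferiority power exceeds 90% and the shortfall shrinks.

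**The case against.** **All-must-pass is a reading, not a stated rule.** This stands. Section 5.2 names no score, so the 90% could belong to one pooled score or to the clarity score that section 6.2 also collects. A reader might infer that the 90% can only be a per-item figure; the documents do not settle that. But neither alternative is defined as the primary endpoint, and clarity is not in the list in section 5.3, so something is missing on every reading.

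**The correlation range is the reviewer's choice.** This stands too. A reader might take 59% to 79% as limits. The 79% only reflects stopping at ρ = 0.8; for non-negative correlation the range is 59% to 90%.

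**The type of test is not wide open.** Largely right. The one-sided test in section 5.2 and the wording of section 5.3 point to non-inferiority, although the hypotheses in section 5.2 are phrased as equivalence. A reader might go further and infer that an equivalence test would probably fail if OCT were somewhat better. The documents do not support that: it needs a margin and a true difference for each item, and they give neither. Nor is there ground for assuming the same shift on all five items, since section 1 describes different strengths for the two modalities.

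**Illegible images.** Section 5.2 says "recognizing that some images (~ 5%) may be of poor quality and illegible, 25 subjects should be enrolled and 115 images evaluated". A reader might infer that illegible images are dropped, in favour of whichever device produces more of them. No section says they are dropped, and the worst grades in section 6.2 already describe very poor images. That inference forms no part of this point.

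**The missing margin is more basic.** True: without it neither 90% nor 59% can be checked. The fix therefore asks for margins together with the combination rule.

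**Conclusion.** The point holds as a mismatch between the stated power and the most natural reading of the success rule. Under that reading the 90% is not the power for the primary endpoint, and the documents give no figure that is. The size is conditional: 59% if items are independent, about 71% at a correlation of 0.5 and 79% at 0.8 under non-inferiority, with 90% only at perfect correlation. It rests on 90% per item at zero true difference, 108 gradable pairs for every item, and independent pairs. It does not show that the trial is likely to fail, and it would fall away if a single defined score were the primary endpoint. It should be corrected, with medium confidence, because the rule itself is left unstated.

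**What to change.** Settle the choice before image reading starts.

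1. If all five items are meant: in sections 5.3 and 6.3 state that every item must pass, each at one-sided 0.05 against a stated margin for that item. Name the type of hypothesis (the current wording points to non-inferiority) and which of the tests in section 6.3 is used. State that grade 1 is best, so that a higher ranking means a lower number. In section 5.2 relabel the 90% as per-item power, and add the joint power with its correlation assumption.
2. If one pooled score or the clarity score is meant: define it as the primary endpoint in sections 5.3 and 6.3, give its margin, and state in section 5.2 that the 90% applies to it.

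The cost is wording in sections 5.2, 5.3 and 6.3, plus the work of justifying margins. No subjects, images or readings are added. Option 1 does not raise power; it makes the stated risk match the rule, so the stated power becomes less favourable.

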#### **5.4. Enrollment and Study Duration**

Subjects will be enrolled at 3 clinical sites in the USA.

Subjects will be considered enrolled into the study once the consent form is signed and the Pantheris catheter is introduced into the vasculature. Subjects will be considered exited from the study once the Pantheris catheter (OCT device) diagnostic imaging and vessel measurements have been completed. Enrollment is expected to start in Q1 2018, and conclude by the end of Q2 2018.

Subjects may withdraw at any time from the study without prejudice or detriment to their medical care. If a subject prematurely terminates from the study, the reason for the termination will be recorded. Subjects who actively withdraw from the trial will be considered “withdrawals.” If termination is a result of an adverse event or death, an Adverse Event Case Report Form will also be completed.

#### **5.5. Duration of Subject Participation**

Participation lasts the duration of the diagnostic imaging procedure. No follow-up imaging or patient data will be collected.

### **6. STUDY PROCEDURE**

#### **6.1 Gathering OCT and IVUS Images**

After providing informed consent, the subject will be prepared for the diagnostic procedure according to the institution’s and investigator’s standard procedures. Demographic information will be recorded for each subject.

A radiopaque ruler will be attached to the subject’s leg to provide reference marks for starting and stopping points of the “target segment” that will be used for image acquisition by the two devices.

Subjects will undergo diagnostic angiographic images to identify the target segment starting point (distal end) and ending point (proximal end) which will be between 5 cm and 10 cm within the vessel.

A 7 Fr vascular sheath will be advanced up-and-over the aortic bifurcation and to the region of interest of the artery.

A 0.014 inch guide wire will be advanced distal to the target segment under angiographic imaging.

An IVUS catheter will be loaded onto the wire and advanced until its imaging transducer resides at the distal end of the target segment (starting point). Using the radiopaque ruler as a reference of the starting point (distal end) and stopping point (proximal end) of the target segment, the IVUS catheter will be energized for imaging and retracted through the target segment (between 5 cm and 10 cm within the vessel) capturing images within the target segment.

The diameter of the lumen of the vessel at the starting, mid, and ending points of the target segment will be measured using the IVUS system software. Mean diameter and luminal area will be calculated for each target segment imaged.

After all images and measurements of the target segment have been captured on the IVUS system, the IVUS catheter will be removed.

Using the radiopaque ruler as a reference, an OCT catheter will be advanced over the 0.014 guide wire until its imaging window is at the exact same starting point (distal end) of the target segment. Once the OCT catheter is inserted, the subject is enrolled in the study. With the device energized, the OCT catheter will be retracted through the exact same target segment of the vessel and the OCT images captured on the Lightbox system.

The diameter of the lumen of the vessel at the starting, mid, and ending points of the target segment will be measured using the OCT system software. Mean diameter and luminal area will be calculated for each target segment imaged.

After all images and measurements of the target segment have been captured on the OCT system, the subject is exited from the study. Once the subject is exited from the study, the investigator can choose to remove the OCT catheter or use it to perform atherectomy.

IVUS images will be collected either on DICOM and stored on a hard drive or saved to an S-VHS and then transferred to a PC hard-drive for processing, per the clinic's standard protocol. OCT images will be captured on the Lightbox and downloaded to a memory stick or external hard drive or DVD.

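### The plan has no position-level OCT–IVUS comparison of lumen diameter, so opposite-sign differences can cancel and the dimension endpoint could be met despite disagreement at matched positions

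*Combined protocol and SAP*

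**What the plan says.** Section 6.1 gives the same instruction for IVUS and for OCT: "The diameter of the lumen of the vessel at the starting, mid, and ending points of the target segment will be measured" with that system's own software. The next sentence defines the derived variables: "Mean diameter and luminal area will be calculated for each target segment imaged". Matched positions are intended, since OCT begins at the same distal point and "the OCT catheter will be retracted through the exact same target segment of the vessel".

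Section 5.3 states the criterion: "Secondary efficacy endpoint is met when OCT imaging has the equivalent dimensions of vessel diameter and total luminal area as that determined with IVUS imaging". It gives no margin, no test and no unit of analysis.

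Section 6.3 contains three methods that could be applied to the dimensions:

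- a matched-pairs t-test, which "will be performed to compare means and on paired samples to compare procedural data" and complications;
- a Mann-Whitney-Wilcoxon test of OCT against IVUS results;
- a Pearson coefficient for the "Correlation of the mean values of the results of the quantitative measurements of all readers with both imaging modalities".

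The intraclass correlation in 6.3 is for reproducibility between and within readers, not for OCT against IVUS. Nowhere does the plan describe a position-by-position comparison, limits of agreement, or a look at the difference against lumen size.

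**The concern.** The design goes to some trouble to match positions, with a radiopaque ruler and the same start and stop points for both catheters. A lumen diameter describes one place in the vessel, so what matters is whether the two devices agree there. The only dimensions the plan derives are segment summaries, and the only analyses it lists compare average level or measure association. None of these can show whether the devices agree at a given position.

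What is at stake is the meaning of the secondary endpoint. It could be declared met when OCT reads larger than IVUS in one part of the segment and smaller in another. Section 2.1 gives a vessel range of 3 to 7 mm for the Pantheris. A 0.6 mm error is 20% of the diameter at 3 mm (0.6/3) and about 9% at 7 mm (0.6/7).

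**Working it through.** **The plan's own figure.** Section 5.2 states 108 image pairs for 90% power at one-sided 0.05. No sample size or power is given for diameter or area. The 108 cannot be reproduced, because neither a margin nor an SD is stated. It implies a margin of (1.645 + 1.282)/√108 = 0.282 SDs of the paired difference for a one-sided non-inferiority test. For two one-sided equivalence tests at zero true difference, the ratio is (1.645 + 1.645)/√108 = 0.317. Neither ratio bears on the present point.

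**Cancellation.** Let d be OCT minus IVUS at a position.

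- With d = −0.3, +0.6, −0.3 mm, the segment-mean difference is (−0.3 + 0.6 − 0.3)/3 = 0.
- With IVUS 5, 5, 5 mm and OCT 6, 5, 4 mm, both means are 5.0 mm. The mean absolute difference is (1 + 0 + 1)/3 = 0.67 mm, and the devices differ by 1 mm at two of three positions.
- With all positions present, the average of all position differences equals the average of the segment-mean differences. A pooled mean-difference test therefore cancels in the same way.

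**The other listed methods.** In the second example, a Mann-Whitney comparison of the three readings gives (3 wins + 3 ties × 0.5)/9 = 0.5, which is no shift. Pearson correlation is also uninformative about agreement. If OCT equalled IVUS plus a constant 0.5 mm in every segment, the coefficient would be 1.

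**Spread.** If position-level differences within a subject have correlation r, the SD of the segment-mean difference relative to the position-level SD is √((1 + 2r)/3). The documents give no r, so a range is assumed.

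| r | ratio | segment-mean limits narrower by |
|---|---|---|
| 0 | √(1/3) = 0.577 | 42% |
| 0.3 | √(1.6/3) = 0.730 | 27% |
| 0.5 | √(2/3) = 0.816 | 18% |

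**Simulation under assumed inputs.** One segment per subject, 25 subjects, bias +b, 0, −b mm at start, middle and end, between-subject SD 0.2 mm, within-subject SD 0.3 mm, and equivalence by two one-sided 0.05 tests. The values tried were b = 0.5 and 1.0 mm, with margins of 0.25 and 0.5 mm. In each case the bias at the two ends is at or beyond the margin.

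| Test | Trials declaring equivalence |
|---|---|
| Segment means | 99.7% to 100% |
| All positions pooled, clustering ignored | 86% to 100% |
| Required at each position | 0% to 0.1% |

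The half-width of the 95% limits of agreement was about 0.51 mm on segment means. On position pairs it was about 1.07 mm (b = 0.5) and 1.76 mm (b = 1.0).

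**Size-dependent error.** If d = a + k × lumen size at each position, averaging gives mean d = a + k × mean lumen size. The slope k is unchanged, although it is estimated over a narrower range of sizes.

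**Area.** In the 5, 5, 5 against 6, 5, 4 example, area from the mean diameter is 19.63 mm² for both devices. The mean of the three circular areas is 20.16 against 19.63 mm² (+2.7%). Area therefore cancels fully only if it is derived from the mean diameter, and 6.1 does not say how it is derived.

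**The case against.** Several points on the other side stand.

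- **The tested variable is inferred.** A reader might conclude that the plan tests segment means. Section 5.3 names only diameter and total luminal area, 6.1 also requires the three individual diameters, and the averaging that 6.3 describes for quantitative measurements is over readers. The segment mean is the only derived diameter, so the inference is natural, but what the documents establish is that the unit of analysis is unspecified.
- **Averaging is not the root cause.** It is tempting to say that switching from segment means to position pairs would solve the problem. The pooled result above shows that it would not. The weakness is relying on a single mean difference and a correlation.
- **Size-dependent bias is not simply hidden.** A linear size effect keeps its slope in segment means, so differences in vessel size between subjects could still reveal it.
- **The plan contains no limits of agreement.** Nothing in it is 42% too narrow. That figure describes an analysis the plan would have to add.
- **Averaging has a rationale.** Positions are matched by an external ruler over two separate catheter passes. Position-level differences therefore mix device disagreement with registration error, which averaging reduces.
- **The missing margin is a separate and larger gap.** Without it the endpoint has no decision rule at either level.

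These points narrow the claim but do not remove it. Adding a margin to a mean-difference test would leave the cancellation in place. Registration error is a reason to report position-level differences with that caveat, not to omit them.

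**Conclusion.** The point holds in a limited form. The plan collects position-matched diameters but defines no analysis that would show whether OCT and IVUS agree at those positions, and it does not state the unit of analysis for the secondary endpoint. Under a segment-mean comparison, or a pooled mean difference, the endpoint could be met while the devices disagree position by position.

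The cancellation is exact arithmetic. The 18% to 42% range rests on assumed correlations of 0.5 to 0, and the simulated rates rest on assumed biases, SDs and margins. Nothing in the documents indicates that device bias actually changes sign along a segment, so they do not support a claim that the endpoint will be met falsely. A count of 25 segments and 25 × 3 = 75 position pairs assumes 25 subjects with one segment each, and the documents do not fix the number of segments per subject. The issue is worth correcting because it concerns a named endpoint and the remedy is cheap.

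**What to change.** In sections 6.1 and 6.3:

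- State the unit of analysis for the secondary endpoint, and retain the start, middle and end diameters from each device as paired data.
- Fit a mixed model to the paired differences, with position as a factor and a subject random effect (and a segment effect if a subject can contribute more than one). Report the OCT–IVUS difference with its confidence interval at each position.
- Report limits of agreement from position-level differences, allowing for clustering within subject, and plot difference against lumen size.
- Once an equivalence margin is set, judge the position-specific differences and the limits against it, not only the overall device contrast. Keep the segment mean as a supporting summary.
- For luminal area, do the same where area is available at each position. Otherwise say that the area comparison is at segment level only. State how area is derived.
- Reconcile the source of the dimension data: 6.1 uses system software at the procedure, while 6.3 refers to readers' quantitative measurements.

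For diameter the cost is wording and analysis time, because 6.1 already requires the three readings. The limits will be wider than on segment means and will include registration error from ruler-based matching, which the report should acknowledge. Position-level area may not be recorded at present.

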## 6.2 Analysis of Images

The trial will acquire at least 115 matched images for analysis by three independent readers who are experienced radiologists and were not involved in the cases during which these images were captured. Sample images of IVUS and OCT will be reviewed prior to the image assessment to create a consistent nomenclature for the readers when identifying different tissue types with both imaging modalities and standardize the image review process. The images will be anonymized and given a unique identification number prior to assessment by the readers. Since the presentation of IVUS and OCT images are visibly different, the readers cannot be blinded as to which imaging device used to generate the image, but the images will

be provided in a random sequence so that the reader cannot match a specific IVUS image to a specific OCT image at the time of the review.

The readers will view the images and rank each for clarity (using a visual analogue scale or VAS) and identification of vessel morphology and disease pre- and post-procedure.

Qualitative interpretation of OCT and IVUS images will be ranked as follows:  
on) for:

- Layered structure – intima, media, external elastic lamina and adventitia (ranked as 1- clear differentiation of the vessel wall layers, 2- differentiation of at least three vessel wall layers, 3- differentiation of at least two vessel wall layers, and 4- no differentiation of any vessel wall layer);
- Non-layered structure—presence of disease in the vessel structure (a 5-point VAS of 1- excellent histology-like image quality to 5- unacceptably poor image quality);
- Abnormal physiology—dissection/tissue flap/false lumen, thrombus, calcium (a 5-point VAS of 1- excellent histology-like image quality to 5- unacceptably poor image quality);
- Bifurcation of the vessel (1- excellent image, 2- acceptable image, 3- unacceptably poor image quality); and
- Frequency of artifacts (ranked as 1- no artifacts, 2- tolerable/not limiting diagnostic image quality, 3- intense and limits diagnostic image quality).

The results of all readings of both imaging modalities will be used for intrareader and interreader comparison to evaluate the reproducibility and reliability of the respective imaging modality.

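### IVUS images, but not OCT images, may be stored on S-VHS tape, with no record of or adjustment for the route; wherever tape is used, the primary image-quality comparison is at risk of bias towards OCT.

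*Combined protocol and SAP*

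**What the plan says.** Section 6.1 gives two storage routes for the comparator, and the choice follows each clinic's own practice: IVUS images are kept as DICOM on a hard drive "or saved to an S-VHS and then transferred to a PC hard-drive for processing". For the test device it says: "OCT images will be captured on the Lightbox and downloaded to a memory stick or external hard drive or DVD". It names no file format, resolution or compression for OCT.

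Section 6.2 has three radiologists grade the stored images on five items, with low scores better. Two items use "a 5-point VAS of 1- excellent histology-like image quality to 5- unacceptably poor image quality". Another is "Frequency of artifacts (ranked as 1- no artifacts, 2- tolerable/not limiting diagnostic image quality, 3- intense and limits diagnostic image quality". The bifurcation item also grades image quality, and the layer item depends on how many wall layers can be told apart. Readers know the modality ("the readers cannot be blinded as to which imaging device used to generate the image"), and images are shown in random order.

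Section 5.3 sets the success rule: "Primary efficacy endpoint is met when OCT imaging has the equivalent or higher ranking of IVUS imaging". Section 6.3 pools the grades: "The mean values of the results of all readings of all readers will be calculated for comparison of image quality". It has no term, stratum or sensitivity analysis for storage route. The minimum record in section 11.1 includes the device used but not how the image was stored.

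**The concern.** The primary endpoint is the quality of what readers see, so anything that degrades the stored image enters the endpoint directly. S-VHS is an analogue medium. Copying to tape and digitising again can lose detail or add noise, and section 6.1 allows this for IVUS only.

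Two features make such a loss hard to detect or remove later. First, because the route follows clinic practice, tape would be confounded with site, and within a taping site it would be confounded with modality. Second, the route is not recorded for each image, and section 5.5 rules out follow-up imaging, so lost quality could not be recovered.

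Random reading order stops readers matching an IVUS image to its OCT partner. It does nothing about a loss that is already in the file. At stake is whether a favourable primary result could be attributed to the devices rather than to the way IVUS was recorded.

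**Working it through.** **The plan's own figures.** Section 5.2 states 108 images per modality, one-sided 0.05, 90% power, five images per subject, and about 5% illegible.
- Subjects: 108/5 = 21.6, so 22. This agrees with the plan.
- Images after loss: 108/0.95 = 113.7, so 114, against a stated 115. This is close enough.
- The 108 itself cannot be reproduced, because no margin, SD or expected difference is given. Solving backwards, with √108 = 10.392:
  - Paired non-inferiority: margin/SD = (1.645 + 1.282)/10.392 = 0.282.
  - Paired two one-sided tests (TOST) with true equality: margin/SD = (1.645 + 1.645)/10.392 = 0.317.

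**Direction.** Let D = IVUS grade minus OCT grade. Low is better, so a positive D favours OCT. If tape worsens IVUS grades, D rises. Under the section 5.3 rule that moves the result towards success. Under a two-sided equivalence test, which is how section 5.2 words its hypotheses, a rise in D can move the result out of the equivalence range.

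**Size, under assumptions.** The documents give neither the share of IVUS images taped (f) nor the loss per taped image (d, in SDs of the paired difference). Both are assumed below. The shift is b = f × d. Images are treated as independent, so the clustering of five images per subject is ignored.
- Type I error at a non-inferiority margin = Φ(b√108 − 1.645).
- TOST power with true equality = Φ((0.317 − b)√108 − 1.645) + Φ((0.317 + b)√108 − 1.645) − 1.

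| f | d | b | Type I error (nominal 0.05) | TOST power (planned 0.90) |
|---|---|---|---|---|
| 0 | any | 0 | 0.050 | 0.90 |
| 1/3 | 0.1 | 0.033 | 0.097 | 0.88 |
| 1/3 | 0.2 | 0.067 | 0.171 | 0.82 |
| 1/3 | 0.3 | 0.100 | 0.272 | 0.72 |
| 1 | 0.1 | 0.100 | 0.272 | 0.72 |
| 1 | 0.2 | 0.200 | 0.668 | 0.33 |
| 1 | 0.3 | 0.300 | 0.930 | 0.07 |

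Example for f = 1/3, d = 0.2: 0.0667 × 10.392 = 0.693; 0.693 − 1.645 = −0.952; Φ(−0.952) = 0.171. The share f = 1/3 stands for one of the three sites in section 5.4, taken as equal in size.

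**What is not reached.** Section 6.1 has lumen diameters measured in each system's own software, and for IVUS before the catheter is removed. The secondary endpoint should therefore not depend on the storage medium.

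**The case against.** The strongest reply is that an option in the text is not an event. A reader might infer that the comparison is biased, or that every site following the protocol would produce biased data. The documents do not support either reading. DICOM is the other permitted route, no section says that any of the three sites uses tape, and if none does the bias from this source is zero.

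A reader might also infer that OCT stays on a lossless native digital path. Section 6.1 names the console and the media but not the export format or compression, so only the absence of a tape step for OCT is established.

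The effect on grades is not documented either. The introduction already describes IVUS as low in resolution, and the scales have only three to five levels, so tape might change few grades. The readers are experienced radiologists who review sample images beforehand and might recognise some tape artifacts. A claim that all five items would worsen by a given amount cannot be drawn from the documents.

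Finally, bias towards success is not the only possible outcome. Sections 5.2 and 5.3 point to different tests, and with no margin stated the net effect on trial success cannot be determined.

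All of these points stand, and they limit the claim to a conditional risk. They do not remove it: a site can follow section 6.1 exactly, hand readers a degraded comparator, and leave no record that would let the analyst see it.

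**Conclusion.** The concern holds as a conditional risk. The protocol permits a potentially lossy storage route for the comparator only, leaves the choice to each clinic, and neither records it nor allows for it in the analysis. If any site tapes, a loss in recording would favour OCT under the equivalent-or-higher rule, or could cause failure under strict two-sided equivalence.

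The size is unknown. The tabulated error rates (0.05 with no tape, 0.10 to 0.93 over the assumed range of tape use) show that modest losses would matter at this sample size. They are not estimates for this trial, since they rest on assumed f and d, a normal approximation and independent images. The point is confined to the primary image-quality comparison. It is worth settling before imaging starts because the remedy is cheap and no later analysis can restore a degraded image.

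**What to change.** - **Section 6.1:** remove the S-VHS option. Require DICOM or an equivalent digital export at acquisition resolution, without lossy compression, for both modalities. This also closes the gap on OCT export format.
- **CRF:** add one field for the storage route of each image.
- **Section 6.3:** if taped IVUS images are nevertheless collected, keep those pairs in the primary comparison so that the 108-image target is not lost, and pre-specify a digital-only sensitivity analysis of that comparison.

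**Cost.** The change is a sentence or two in 6.1, one in 6.3 and one CRF field. A site with only tape output must enable digital export before enrolling. The sensitivity analysis would be smaller: if one of three equal sites taped, 115/3 is about 38 pairs, leaving 115 − 38 = 77, below 108. At the back-solved non-inferiority margin of 0.282 SD, its power would be Φ(0.282 × √77 − 1.645) = Φ(0.83), about 0.80 instead of 0.90. It is therefore a check on the primary result and not a replacement for it. If all sites already export DICOM, the change costs almost nothing.
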